## 9.13. Success Criteria for Feasibility 2 (Digital Twin and Meal Prediction)

The following criteria will be used to evaluate success of the Feasibility 2:

No occurrence of severe hypoglycemia or DKA due to device algorithm during the feasibility studies

1. Average time with SG below 70 mg/dL of 47 minutes or less (i.e.  $\leq 3.3\%$ ) as in CER294DOC

# 10. Risks and Benefits

## 10.1. Potential Risks

**Table 6. Risks, Prevention and Mitigation**

Risks with Infusion Sets	Prevention and Mitigation

Risks with infusion sets may include:
 

• Localized infection

• Skin irritation/redness

• Bruising

• Discomfort/pain

• Bleeding

• Irritation

• Rash

• Hyperglycemia secondary to infusion set occlusion or infusion site failure including DKA

• Hyperglycemia secondary to site falling off including DKA

• Anxiety associated with insertion

	
Prevention and mitigation include:
 

• Follow the provided user guides for insertions and care of infusion sets.

• If an infusion site becomes irritated or inflamed, the infusion set will be removed and another placed in a new location.

• In case of hyperglycemia secondary to infusion set occlusion, remove current infusion set and replace with new infusion set and give correction insulin if needed with syringe.

• Follow the provided user guides for insulin pump management.

• Train prior to study device use on appropriate device use and diabetes management principles and instruct to call investigator with problems.

Risks with Insulin Administration and Pumps	Prevention and Mitigation

Risks with the use of an insulin infusion pump may include the risk of malfunction of the components of the system (pump, software, infusion set and reservoir) as well as the risk of use error during use of the system. Device deficiencies or use errors can result in administration of too much or too little insulin which can lead to the following clinical consequences:
 

• Hypoglycemia

• Hyperglycemia

• Diabetic ketoacidosis

• Severe hypoglycemia with or without associated seizure, coma or death

• Kinked cannula leading to hyperglycemia

• Infusion set disconnection from pump leading to hyperglycemia

• Subject removes the reservoir from the pump but forgets to disconnect the infusion set from the body which results in hypoglycemia or severe hypoglycemia

• Dislodged cannula leading to hyperglycemia

• A pump error may lead to under delivery or over-delivery of insulin

• Battery failure – no insulin delivered

	
Prevention and mitigation include:
 

• Follow the provided user guides& instructions for insulin pump management which includes information on infusion set change.

• Train prior to study device use on appropriate device use and diabetes management principles and instruct to call investigator with problems.

• Check SMBG 4-6 times a day and also before driving (as applicable).

• Instruct to have glucose on hand for hypoglycemia

• Instruct to change infusion set if suspected catheter occlusion or administer insulin with syringe for persistent hyperglycemia especially if ketones develop.

• Parent(s)/guardian(s)/companion(s) will be present at night with subjects and will be trained on study device and diabetes management principles and instructed to call investigator with problems.


 
• Insulin deterioration leading to hyperglycemia
 
• Incomplete priming; fails to prime tubing and/or cannula, leading to hyperglycemia
 
• Remove a reservoir, without suspending and reconnecting after a while resulting in a Hypoglycemia
 
• Patient not filling pump reservoir when needed leading to hyperglycemia
 
• Magnetic Resonance Imaging resulting in pump/transmitter malfunction
 
• Inaccurate insulin delivery due to sudden altitude changes.
 
• Hypoglycemia or hyperglycemia from manual bolus
 
• Hypoglycemia or hyperglycemia from computer hacking
 
	

Risks with hyperglycemia may include
 
 
• Diabetic ketoacidosis
 
• Symptomatic ketosis
 
• Cardiovascular event
 
• Dehydration
 
• Potassium and sodium imbalance
 
• Shock
 
• Altered mental status
 
• Coma
 
• Acidosis
 
	
Prevention and mitigation include:
 
 
• Follow the provided user guides for insulin pump management.
 
• Parent(s)/guardian(s)/companion(s) will be present at night with subjects and will be trained on study device and diabetes management principles and instructed to call investigator with problems.
 
• Train prior to study device use on appropriate device use and diabetes management principles and instruct to call investigator with problems.
 
• Check SMBG 4-6 times a day.
 
• Alternative method of managing glucose levels will be available (insulin and syringe for example)
 


Risks with hypoglycemia may include:
 
 
• Seizure
 
• Coma
 
• Altered mental status
 
• Loss of consciousness
 
• Cardiovascular event
 
• Death
 
• Risk of rebound hyperglycemia with ketosis
 
	
Prevention and mitigation include:
 
 
• Follow the provided user guides for insulin pump management.
 
• Parent(s)/guardian(s)/companion(s) will be present at night with subjects and will be trained on study device and diabetes management principles and instructed to call investigator with problems.
 
• Train prior to study device use on appropriate device use and diabetes management principles and instruct to call investigator with problems.
 
• Check SMBG 4-6 times a day.
 
• Instruct to have glucose on hand for hypoglycemia
 

Risk with Sensors	Prevention and Mitigation

Risks with Sensors may include:
 
 
• Skin irritation or reaction to adhesives
 
• Bruising
 
	
Prevention and mitigation include:
 
 
• Follow the provided user guides for insertions and care of sensors.
 



• Discomfort

• Redness

• Bleeding

• Excessive bleeding due to anticoagulants

• Pain

• Rash

• Infection

• Irritation from tapes used with glucose-sensing products

• Raised bump

• Appearance of a small "freckle-like" dot where needle was inserted

• Allergic reaction

• Syncopal episode secondary to needle insertion

• Soreness or tenderness

• Swelling at insertion site

• Sensor fracture, breakage or damage

• Minimal blood splatter associated with sensor needle removal

• Residual redness associated with adhesive and or tapes

• Scarring

• Scab

• Blister

• Itchiness

• Inflammation

• Anxiety

• Incorrect sensor glucose reading results in incorrect diabetes management

• Subject over-treating secondary to alarms which can result in hyperglycemia or hypoglycemia

• Anxiety associated with insertion

	

• If a sensor site becomes infected or inflamed, the sensor will be removed and another placed in a new location

• Base diabetes management on fingerstick readings and not sensor glucose values.

Risks with Transmitter	Prevention and Mitigation
Risks with Transmitter may include: 

• Skin irritation or reaction to adhesives

• Bruising

• Discomfort

• Redness

• Pain

• Rash

• Infection

• Irritation from tapes used with glucose-sensing products

• Raised bump

• Allergic reaction

• Soreness or tenderness

• Residual redness associated with adhesive and/ or tapes

• Scarring

• Scab

	Prevention and mitigation include: 

• Follow the provided user guides.

• Train on the proper use of the transmitters.

• Blister

• Itchiness

• Inflammation

	
Risks with Serter	Prevention and Mitigation
Risks with serters may include: 

• Improper insertion may lead to device performance issue or hyperglycemia

	Prevention and mitigation include: 

• Follow the provided user guides for insertions and care of device.

• Train on the proper use of the serter and skin preparation prior to insertion.

Risks with Finger Sticks	Prevention and Mitigation
Risks with frequent finger stick testing may include: 

• Potential risks associated with frequent meter testing of blood glucose and blood ketones include discomfort and ecchymosis at tips of fingers

• Potential risks associated with finger stick testing include discomfort and bruising

	Prevention and mitigation include: 

• Follow the provided user guides for use of the study meter with fingerstick testing.

• Train on the proper use of the study meter and fingerstick testing.

Risk with Closed Loop Therapy	Prevention and Mitigation

Risks with Closed Loop may include:
 

• Hypoglycemia

• Severe hypoglycemia

• Hyperglycemia

• Diabetic ketoacidosis

• User Entry Error

◦ Patient administering boluses by entering false carb doses leading to hypoglycemia or hyperglycemia

◦ Patient entering false glucose values for any reason leading to hypoglycemia and hyperglycemia

◦ Patient entering false BG values for calibration leading to hypoglycemia or hyperglycemia

• Sensor failure resulting from patient failure to calibrate leading to hypoglycemia or hyperglycemia

• Sensor over-reading resulting in hypoglycemia

• Sensor under-reading resulting in hyperglycemia

• Sensor missed transmission, or any other fault resulting in no SG value, leading to hyperglycemia or hypoglycemia

• Voluntary insulin delivery (with the pump or with a syringe) immediately prior to entering Auto Mode may result in severe hypoglycemia despite shutting down insulin delivery by the algorithm

• Meal prediction algorithm CHO recommendations may be too high or too low, potentially leading to hypoglycemia or hyperglycemia

• Hypoglycemia related to patient taking insulin via injection while in Closed Loop (Auto Mode)

	
Prevention and mitigation include:
 

• Follow the provided user guides for insulin pump management.

• Train prior to study device on appropriate device use and diabetes management principles and instruct to call investigators with problems.

• Check SMBG 4-6 times a day.

• Instruct to have glucose on hand for hypoglycemia

• Instruct to avoid the use of products containing acetaminophen

• If acetaminophen is taken, subjects will be instructed to use additional BG meter readings (they are not to calibrate with those readings) to verify their glucose levels.

• If acetaminophen is taken, subjects will exit Auto Mode

• Pump has cybersecurity encryptions to prevent hacking.

 
Hypoglycemia or hyperglycemia related to entering or exiting Closed Loop (Auto Mode)
 
Insulin over-delivery due to acetaminophen
 
Cyber security hacking into pump
 
	
Risks with hyperglycemia may include 
 
Diabetic ketoacidosis
 
Symptomatic ketosis
 
Cardiovascular event
 
Dehydration
 
Potassium and sodium imbalance
 
Shock
 
Altered mental status
 
Coma Acidosis
 
	Prevention and mitigation include: 
 
Follow the provided user guides for insulin pump management.
 
Train prior to study device use on appropriate device use and diabetes management principles and instruct to call investigator with problems.
 
Check SMBG 4-6 times a day.
 

Risks with hypoglycemia may include: 
 
Seizure
 
Coma
 
Altered mental status
 
Loss of consciousness
 
Cardiovascular event
 
Death
 
Risk of rebound hyperglycemia with ketosis
 
	Prevention and mitigation include: 
 
Follow the provided user guides for insulin pump management.
 
Train prior to study device use on appropriate device use and diabetes management principles and instruct to call investigator with problems.
 
Check SMBG 4-6 times a day.
 
Instruct to have glucose on hand for hypoglycemia
 

Risk with Acetaminophen Use	Prevention and Mitigation
Potential risks with acetaminophen may include: 
 
False elevation of sensor glucose readings. The level of inaccuracy depends on the amount of acetaminophen active in subject's body and may be different for each subject
 
Liver damage, liver failure and/or rare but fatal liver failure can occur
 
Skin rash and/or serious and potentially fatal skin reactions have been reported
 
Allergic reactions including those which are serious and potentially fatal can occur
 
Kidney disease
 
Lowered blood counts (red cells, and white cells)
 
	Prevention and mitigation include: 
 
Follow the user guide
 
Instruct to avoid the use of products containing acetaminophen
 
If acetaminophen is taken, subjects will be instructed to use additional BG meter readings (they are not to calibrate with those readings) to verify their glucose levels
 
Subjects will exit Auto Mode
 

Risk related to Algorithms	Prevention and Mitigation
Digital Twin Algorithm: 

• Frequent transition between Manual Mode and Auto Mode could introduce bias in the algorithm adaptations.

• Lifestyle and physiological changes

• Unannounced meals could introduce error in carb ratio estimation by the algorithm

	

• User historical data from system use in both pump modes (Auto Mode and Manual Mode) are used to generate a user's digital twin.

• The amount of historical data (insulin delivery, SG values, meals/carb estimates) must be sufficient for a digital twin to be generated.

• The Digital Twin algorithm is designed to absorb drastic lifestyle changes by providing therapy adaptations that are constrained by common insulin therapy heuristics or by safeguards of the pump's advanced hybrid closed loop (AHCL) insulin delivery algorithms

• The Digital Twin algorithm simulates the total daily insulin delivery (TDD) after generating each adaptation of pump settings. If the simulated TDD is more than 50% greater or less than the TDD recorded in CareLink, the algorithm will not provide any therapy adaptations

• The algorithm can detect meal events from historical data, even if the meals are not announced. If there are fewer than 2 meal events per day, on average, in the historical data set, whether the meals were announced or detected within the data, the Digital Twin algorithm does not generate a digital twin. When no digital twin of the patient is generated, no new adaptations to pump settings will be generated.

• The primary mitigation is that the physician must review and approve all device setting recommendations.

Meal Prediction Algorithm: 

• Inaccurate carb estimate predictions (either higher or lower than the amount of CHO to be consumed) could lead to under- or over-delivery of insulin

• Inaccurate meal time predictions could lead to nuisance or promotion of pre-mature meal bolus delivery

	

• The user will approve the amount of carbohydrate recommended by the meal prediction algorithm

• No automated boluses are given. The user will approve all insulin given with meal.

## 10.2. Risk Minimization

Refer to "Prevention and Mitigation" column in the table under Section 10.1.

## 10.3. Potential Benefits

Subjects may experience improved glucose control. However, subjects may not benefit from participation in this study; they may gain increased awareness of emerging technologies for diabetes management as a result of their participation.

## 10.4. Risk-Benefit Rationale

The main benefit of this study is that patients are likely to experience improved glucose control. The primary risk, as with all automated insulin delivery systems, is the possibility of an increase in hypoglycemia. To address this risk, many scenarios have been modeled and, the risk is effectively minimized by a variety of safety checks that are an integral part of the new cloud algorithms and the revised insulin delivery algorithm.

## 10.5. Risk Determination

In the opinion of the sponsor, this study is considered a significant risk (SR) study. Subjects in the study will use the MiniMed 670G 4.0 Pump, an investigational device that is intended for use of substantial importance in treating diabetes and presents a potential for serious risk to the health, safety, or welfare of a subject. Per 21 CFR 812.3(m)(3), this device is a significant risk device.

Other investigational devices in the study include the cloud-based Digital Twin and Meal Prediction algorithms and the App. The Digital Twin algorithm is intended to provide pump settings recommendations based on individual patient data, which will be reviewed and approved by the investigator prior to implementation on a subject's pump. The Meal Prediction algorithm is intended to provide meal time notifications to the subject via the mobile application on the subject's Smartphone. The App is intended for meal logging and acknowledgment of meal time notifications by the subject. In this study, these 3 investigational devices function as accessories to, but do not communicate directly with, the MiniMed 670G 4.0 Pump.

All other devices used during this investigation have been previously approved by FDA for commercial distribution in the United States.

Considering the above discussion, and per 21 CFR 812.2, the devices above require application for an investigational device exemption.

## 11. Adverse Events Assessments

### 11.1. Adverse Events

Throughout the course of the study, investigational centers will make all efforts to remain alert to possible reportable adverse events (AEs) or untoward findings. The study personnel will elicit reports of AEs from the subject at each visit (including phone calls) starting at the time of signing the informed consent documenting the medical diagnosis, date of event start and end, causality (relationship to device or procedure), treatment, outcome, and description that includes the details of the event.

### 11.2. Definitions and Classification of Adverse Events

Medtronic uses the definitions provided in ISO 14155:2020 and 21 CFR 812 for AE definitions. Where the definition indicates "device", it refers to any device used in the study. This might be the device under investigation, or any market released component of the system.

**Severe Hypoglycemia** is an event requiring assistance of another person due to altered consciousness to actively administer carbohydrate, glucagon, or other resuscitative actions. This means that the subject was impaired cognitively to the point that he/she was unable to treat himself or herself, was unable to verbalize his or her needs, and was incoherent, disoriented and/or combative.

These episodes may be associated with sufficient neuroglycopenia to induce seizure or coma. Plasma glucose measurements may not be available during such an event, but neurological recovery attributable to the restoration of plasma glucose to normal is considered sufficient evidence that the event was induced by a low plasma glucose concentration. (**Adapted from American Diabetes Association Workgroup on Hypoglycemia, Diabetes Care 28:1245-1249, 2005**)

**Severe Hyperglycemia** is defined as hyperglycemia (blood glucose greater than ( $>$ ) 300 mg/dL or 16.7 mmol/L) with blood glucose ketones greater than ( $>$ ) 1.5 mmol/L, urine ketones moderate or large, or accompanied by symptoms of nausea, vomiting or abdominal pain.

**Diabetic Ketoacidosis/DKA diagnostic criteria:** blood glucose greater than ( $>$ ) 250 mg/dL or greater than ( $>$ ) 13.9 mmol/L, arterial pH less than ( $<$ ) 7.3, bicarbonate less than ( $<$ ) 15 mEq/L, moderate ketonuria or ketonemia and requiring treatment within a health care facility. (**American Diabetes Association-Diabetes Care, Volume 27, Supplement 1, January 2004; S94-S102**)

Hyperglycemic events will be recorded as DKA if the event includes the presence of all of the following:

- Arterial blood pH less than ( $<$ ) 7.30 or serum bicarbonate less than ( $<$ ) 15 mEq/L
- Blood glucose greater than ( $>$ ) 250 mg/dL or greater than ( $>$ ) 13.9 mmol/L
- Serum ketones or large/moderate urine ketones
- Symptoms such as polyuria, polydipsia, nausea, or vomiting
- Treatment provided in a health care facility

## Adverse Event (AE) (ISO 14155:2020)

Any untoward medical occurrence, unintended disease or injury, or untoward clinical signs (including abnormal laboratory findings) in subjects, users or other persons, whether or not related to the investigational medical device and whether anticipated or unanticipated.

**Note 1 to entry:** This definition includes events related to the investigational medical device or the comparator.

**Note 2 to entry:** This definition includes events related to the procedures involved.

**Note 3 to entry:** For users or other persons, this definition is restricted to events related to the use of investigational medical devices or comparators.

## Adverse Device Effect (ADE) (ISO 14155:2020)

Adverse event related to the use of an investigational medical device.

**Note 1 to entry:** This definition includes adverse events resulting from insufficient or inadequate instructions for use, deployment, implantation, installation, or operation, or any malfunction of the investigational medical device.

**Note 2 to entry:** This definition includes any event resulting from use error or from intentional misuse of the investigational medical device.

**Note 3 to entry:** This includes 'comparator' if the comparator is a medical device.

## Serious Adverse Event (SAE) (ISO 14155:2020)

Adverse event that led to any of the following

- a) death,
- b) serious deterioration in the health of the subject, users, or other persons as defined by one or more of the following:
  1. a life-threatening illness or injury, or
  2. a permanent impairment of a body structure or a body function including chronic diseases, or
  3. in-patient\* or prolonged hospitalization, or
  4. medical or surgical intervention to prevent life-threatening illness or injury or permanent impairment to a body structure or a body function,
- c) foetal distress, foetal death or a congenital abnormality or birth defect including physical or mental impairment

**Note 1 to entry:** Planned hospitalization for a pre-existing condition, or a procedure required by the CIP, without serious deterioration in health, is not considered a serious adverse event.

*\*For the purpose of this study, Inpatient Hospitalization is defined as: admission to the hospital for a period of 24 hours or more based on urgent medical need rather than elective admission.*

For the purpose of this study, the term "life-threatening" in the definition of "serious" refers to an event in which the patient was at risk of death at the time of the event; it does not refer to an event which hypothetically might have caused death if it were more severe. (ICH Topic E 2 A Clinical Safety Data Management: Definitions & Standards for Expedited Reporting. EMEA 2006)

### **Serious Adverse Device Effect (SADE) (ISO 14155:2020)**

Adverse device effect that has resulted in any of the consequences characteristic of a serious adverse event.

### **Unanticipated Adverse Device Effect (UADE) (21 CFR 812.3(s))**

Any serious adverse effect on health or safety or any life-threatening problem or death caused by, or associated with, a device, if that effect, problem, or death was not previously identified in nature, severity, or degree of incidence in the investigational plan or application (including a supplementary plan or application), or any other unanticipated serious problem associated with a device that relates to the rights, safety, or welfare of subjects.

## **11.3. Reporting of Adverse Events**

The investigator or designee will record ALL AEs while the subject is enrolled in the clinical study.

Each AE needs to be assessed for its device or procedure relatedness. A device related AE is associated with the use of the study device (e.g. infection of sensor site or infusion set occlusion resulting in DKA). A procedure related AE is associated with testing related to the study procedures specified in the CIP (e.g. IV insertion pain).

Examples of device or procedure related AEs include:

- **Device** related (ADE): insertion site infection
- Serious adverse **device effect** (SADE): cellulitis at device insertion site requiring hospitalization
- **Procedure** related AE: bruising at IV insertion site

Subjects participating in the study have diabetes and are expected to experience hypoglycemia and or hyperglycemia. These normal events are not expected to be reported to sponsor as this is not considered an untoward event, but rather an expected occurrence. Any glycemic excursion that meets the protocol definition of Severe Hypoglycemia, Severe Hyperglycemia or DKA is considered an untoward event and a worsening from the subject's baseline and would be reported to sponsor on an AE eCRF.

Baseline medical conditions should only be reported to sponsor on an AE eCRF if there is a worsening from the subject's baseline. For example, a subject previously diagnosed with Asthma is hospitalized for severe asthma attack would be a reportable event.

Adverse events will be documented in the subject source file and reported to sponsor on an eCRF. The investigational center is responsible for documentation of AEs including obtaining source documents related to the event, such as emergency medical technician/paramedic reports, hospital records (admission summary; lab results, test results, discharge summary) or device uploads to support the

event. Source documents will be reviewed to determine if additional AEs have occurred and require reporting.

Adverse events that have not resolved at the time of the subject's discontinuation or completion of the study should have an "outcome" of Not Recovered/Not Resolved at study end in subject source and on an eCRF. The investigator should ensure that subject is aware of any follow-up or additional treatment that is required for any ongoing AE at end of study participation; however, there will be no eCRF entry for the ongoing follow-up.

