## 9.10. Subject Exit, Withdrawal or Discontinuation

Subjects may choose to withdraw from the study at any time by notifying investigational center staff of their intent.

If a subject chooses to end his or her study participation or if the subject is removed from the study at the Investigator's discretion or for failure to meet the study requirements, the reason for withdrawal must be documented. All study devices and supplies must be returned (as applicable) and documented both in source documents and on an eCRF.

Subjects may also be withdrawn from the study at the discretion of the Investigator. A subject will be withdrawn from the study if:

- In the opinion of the investigator, the subject's health or safety would be compromised by continuing in the study
- In the opinion of the investigator, it is in the subject's best interest to discontinue participation in the study
- During the course of the study, subject begins participation in another investigational study (drug or device).
- Subject participates in a phase that requires a Smartphone as part of the study requirements and subject does not have a Smartphone.
- During the course of the study, subject begins abusing illicit drugs.
- During the course of the study, subject begins abusing alcohol.
- During the course of the study, subject begins using pramlintide (Symlin), DPP-4 inhibitors, liraglutide (Victoza or other GLP-1 agonists), metformin, canagliflozin (Invokana or other SGLT2 inhibitors).
- During the course of the study, the subject demonstrates that he/she is not able to comprehend instructions for study procedures, as evaluated by the appropriate research staff.
- During the course of the study, subject is taking oral, injectable, or IV glucocorticoids
- During the study, (female) subject becomes pregnant.
- During the study, the subject experiences one severe hypoglycemic episode
- During the study, the subject experiences one episode of DKA
- During the study, subject has a cardiovascular event or any vascular event such as stroke.

Documentation of the reason(s) leading to subject withdrawal will be kept in the subject's source documentation.

For **Study Exit** visits for reason other than subject lost to follow-up, the following information is required:

- Assess and document any reportable AEs (refer to section 10 Adverse Events)
- For study exit visits occurring in the clinic, perform a CareLink™ upload

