## 9.11. Subject Stopping Rules

Any episode of DKA or severe hypoglycemia will result in withdrawal of subject from study.

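### A serious event still open when the subject is withdrawn keeps the outcome Not Recovered/Not Resolved, because section 11.3 allows no later eCRF entry

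*Protocol*

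**What the plan says.** Protocol section 9.10 lists events after which a subject will be withdrawn. Four are health events:

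- severe hypoglycemia, after a single episode
- DKA, likewise after a single episode
- a vascular event, worded as "During the study, subject has a cardiovascular event or any vascular event such as stroke"
- pregnancy, worded as "During the study, (female) subject becomes pregnant"

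Section 9.11 repeats the first two as a rule without discretion: "Any episode of DKA or severe hypoglycemia will result in withdrawal of subject from study".

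Section 11.3 sets the recording window: "The investigator or designee will record ALL AEs while the subject is enrolled in the clinical study". An event unresolved at discontinuation or completion is given the outcome Not Recovered/Not Resolved, in source and on the eCRF. The investigator makes sure the subject knows what further care is needed; "however, there will be no eCRF entry for the ongoing follow-up".

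The serious adverse event (SAE) definition in section 11.2 includes death, permanent impairment and "foetal distress, foetal death or a congenital abnormality or birth defect including physical or mental impairment".

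**The concern.** Evaluating subject safety is the study's stated purpose (Protocol 3.2, SAP 3.2). The events of most safety interest are also the ones that end participation, and the end of participation fixes the recorded outcome of anything still open. A stroke or a long DKA admission may be unresolved at exit, and how it ended may be known only weeks later. At stake is the outcome field for a handful of serious events, in a study that the sponsor rates as significant risk (10.5) and that enrolls children from 2 years of age (7.3). With few such events expected, each outcome carries weight.

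**Working it through.** No figure in the plan bears on this and no arithmetic applies. The check follows the text in order.

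1. **Is withdrawal mandatory?** Yes. The 9.10 list is worded as mandatory, and 9.11 confirms this for DKA and severe hypoglycemia. For vascular events and pregnancy it rests on the 9.10 list alone.

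2. **What is recorded at exit?** Section 9.1 asks for the final-visit requirements. Section 9.10 asks for an adverse event assessment and a CareLink upload. Neither ties the timing of the exit visit to resolution of the event, and neither lists a later contact.

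3. **What can be recorded after exit?** Under 11.3, no follow-up of an open event. Setting the possible courses side by side:

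| Course of the event | Outcome in the eCRF |
|---|---|
| Resolves before exit | Actual outcome |
| Open at exit, later recovers | Not Recovered/Not Resolved |
| Open at exit, later permanent impairment | Not Recovered/Not Resolved |
| Open at exit, later death | Not Recovered/Not Resolved |

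The last three rows cannot be told apart.

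4. **Does another section restore follow-up?**
 - Sections 11.3 and 11.4 have the site obtain hospital records, including discharge summaries, and send supporting documents to the sponsor.
 - Section 12.1 lets the CEC delay its disposition until such records arrive. It has the form updated when the investigator accepts a CEC reclassification.
 - Section 9.12 has the sponsor keep FDA updated on stopping-rule events.
 - Section 11.5 starts the clock for reporting an unanticipated adverse device effect (UADE) when the investigator learns of the event.
 - SAP 7.4 tabulates available data without imputation, and SAP 7.10 lists the safety endpoints; neither adds follow-up.

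 None of these requires follow-up to a final outcome or permits its entry on the eCRF.

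5. **Which planned results depend on the missing outcome?** None. The safety endpoints (Protocol 14.4.2, SAP 7.10) are severe glycemic events and a summary of adverse events. The suspension rule in 9.12 counts algorithm-related events (2 or more DKA, or 4 or more severe hypoglycemia). The first success criterion in 9.13 is that no algorithm-caused event occurs. The triggering event is recorded in every case.

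6. **Pregnancy.** The 11.3 sentence covers adverse events already open at exit, and pregnancy is not itself listed as one. The gap here comes from the enrollment window combined with forced withdrawal. Foetal outcomes would mostly arise after exit, so that part of the SAE definition is largely unobservable.

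**The case against.** The strongest reply is that the end of a hospital admission is not lost. Discharge records are requested, go to the sponsor and are among the CEC's inputs. No planned analysis uses outcome or duration. Severe hypoglycemia is usually brief and may well have resolved by the exit visit, in which case its true outcome is recorded. All of this stands, and it limits the point to the structured outcome of events open at exit and to sequelae after discharge.

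A reader might infer more than the documents support in four ways:

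- *That CEC classification and UADE assessment hinge on how an event ends.* CEC review turns mainly on cause (12.1). UADE status turns on whether the effect was already identified (11.2), and coma, cardiovascular event and death are listed risks (10.1). Seriousness is usually met at onset, through threat to life, admission or intervention.
- *That severity is systematically understated.* The fixed code overstates persistence for an event that later resolves. It understates only later death or lasting harm.
- *That the planned shortfall of 200 − 150 = 50 subjects measures the problem.* That is non-completion for any reason, counted from consent (7.2), and says nothing about open serious events.
- *That the quoted sentence causes the pregnancy gap.* It does not; see step 6 of the working.

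**Conclusion.** The point holds in this limited form. For serious events open at exit, an explicit rule keeps a later death or permanent impairment out of the adverse event outcome data, and no other section puts it back. The number affected cannot be derived from the documents and is probably small. The conclusion assumes that some events will be open at exit; the plan neither prevents this nor times the exit visit to avoid it. Event counts, stopping rules and success criteria stand as planned. The pregnancy gap is separate and rests on the enrollment window and the absence of any provision for pregnancy follow-up. This is an inexpensive improvement to safety data collection; it does not undermine the planned analyses.

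**What to change.** In section 11.3, exempt the following from the rule when they are open at exit: SAEs, serious adverse device effects, UADEs, severe hypoglycemia, DKA and cardiovascular or vascular events. For these, have the site update the outcome on the existing adverse event eCRF until resolution, stabilisation or a fixed cut-off, for example 30 days after exit, and send the final outcome to the CEC. Keep the current rule for all other adverse events. Separately, add a follow-up contact to record the pregnancy outcome of any subject withdrawn for pregnancy. While amending, correct the exit-visit list in 9.10, which refers to section 10 for adverse events although they are covered in section 11.

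The change concerns data collection only and leaves the withdrawal criteria as they are. It costs a short amendment, a few follow-up contacts and a slightly later data lock for affected subjects.
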